## **6.2 Efficacy Analysis**

### **6.2.1 Analysis Population**

The population for the analysis of efficacy endpoints will be all subjects who have received at least 1 dose of BG00012 in this study and who have an evaluation of the efficacy endpoint under analysis.

### **6.2.2 Analysis Methods**

Summary statistics will be presented for MRI data (number of new or newly enlarging T2 hyperintense lesions) over time

ARR will be summarized, along with the proportion of subjects relapsing, the rate of relapses requiring IV steroid use, and the rate of MS-related hospitalizations.

EDSS scores and changes from baseline will be summarized over time along with the proportion of subjects with confirmed disability progression.

## **6.3 Safety Data**

### **6.3.1 Analysis Population**

The analysis population for safety summaries will be all subjects who received at least 1 dose of BG00012.

### **6.3.2 Analysis Methods**

Summaries of safety data will include descriptive statistics for continuous variables and frequency distributions for categorical variables.

#### **6.3.2.1 Definition of Baseline Value and Visit Windows**

Baseline values and visit windows for safety summaries are defined in the same way as they are for efficacy analyses (see Section 6.1.1 and 6.1.7, respectively).

### **6.3.2.2 Clinical Adverse Events**

Treatment (BG00012)-emergent AEs are defined as AEs occurring or worsening after beginning study treatment (after the first dose in study 109MS311).

Incidence of AEs will be summarized using frequency distribution tables; overall, by severity, and by relationship to BG00012. The summary tables will include incidences for system organ class as well as for preferred terms within each system organ class. Similar incidence analyses will be summarized for SAEs and for the most common AEs.

AEs will be coded using the MedDRA dictionary (version 20.1). This coding system provides five levels to classify AEs. In general, AEs will be presented by system organ class and preferred term.

The summary tables will include incidence estimates for overall system organ class as well as for preferred terms within each system organ class. AEs will be presented in the order of decreasing incidence of system organ class and then by preferred term within system organ class.

If a subject experiences an event more than once during the study, he/she will be counted only once using the maximum severity if more than one severity is reported, within each system organ class/preferred term.

AEs will be classified by severity (mild, moderate and severe) and by relationship to BG00012.

The incidence of SAEs will be presented by system organ class and preferred term. Details of each SAE will be listed, including subject ID, system organ class/preferred term, date of onset, severity, relationship to BG00012 and action taken. Subject narratives will also be provided.

The incidence of AEs that led to early withdrawal from the study will be presented separately. A listing of the individual subjects with these AEs will also be presented.

The incidence of AEs that led to treatment discontinuation during the study will be presented in a separate table, along with a listing of these individual subjects who experienced AEs leading to treatment discontinuation.

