8.2. Exclusion Criteria

Candidates will be excluded from study entry if any of the following exclusion criteria exist at Day 1 or at the timepoint specified in the individual criterion listed:

1. Unwillingness or inability to comply with study requirements, including the presence of any condition (physical, mental, or social) that is likely to affect the subject's ability to comply with the protocol.
2. Any significant changes in medical history occurring after enrollment in the parent Study 109MS202, including laboratory test abnormalities or current clinically significant conditions that in the opinion of the Investigator would have excluded the subject's participation from the parent study. The Investigator must re-review the subject's medical fitness for participation and consider any factors that would preclude treatment.
3. Subjects from Study 109MS202 who could not tolerate study treatment.
4. History of malignancy.
5. History of severe allergic or anaphylactic reactions or known drug hypersensitivity to DMF or fumaric acid esters.
6. Any of the following abnormal blood tests:
 - ALT >3 times the ULN
 - AST >3 times the ULN
 - Gamma-glutamyl-transferase >3 times the ULN

CONFIDENTIAL

The information contained herein may not be used, disclosed, or published without the written consent of Biogen MA Inc.

- Creatinine >1.2 times the ULN
- WBC count <2000/mm³
- Lymphocyte count <500/mm³

7. Female subjects considering becoming pregnant or breastfeeding while in the study or who are pregnant or breastfeeding.
8. Other unspecified reasons that, in the opinion of the Investigator or Biogen, make the subject unsuitable for enrollment.

CONFIDENTIAL

The information contained herein may not be used, disclosed, or published without the written consent of
Biogen MA Inc.

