15.3. Monitoring and Recording Events

15.3.1. Adverse Events

Any AE experienced by the subject between the time of first dose of study treatment in the extension study and the Safety Follow-Up Visit is to be recorded on the eCRF, regardless of the severity of the event or its relationship to study treatment.

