16.1.2. Methods of Analysis

16.1.2.1. Analysis of the Primary Endpoint

The primary analysis will be summaries of the incidence of treatment-emergent AEs, SAEs, and discontinuations from study treatment due to AEs.

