## **1 STUDY OBJECTIVES AND ENDPOINTS**

### **1.1 Primary Objective and Endpoint**

The primary objective of the study is to evaluate the long-term safety of BG00012 in pediatric subjects who completed Study 109MS202.

Primary endpoint:

incidence of AEs, serious AEs (SAEs), and discontinuations of study treatment due to an AE

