#### **6.1.2 Accounting of Subjects**

Number of subjects who enrolled into 109MS311 from the previous study, number who received at least one dose of BG00012, number completing treatment, number completing the study, number discontinuing prior to Week 96 and reason for early withdrawal, will be summarized.

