#### **6.1.4 Demographic and Baseline Characteristics**

Demographic data, including age (in years, at the time of consent to study 109MS311), gender and race category will be summarized for the subjects that enroll into study 109MS311. In addition, baseline height (cm) and weight (kg) will also be presented.

Medical history will be summarized for just those subjects who enrolled in 109MS311 by category using number and percentage of subjects that had experienced certain maladies prior to entering the study. Medical history will include information collected in 109MS202, but for only those subjects who entered 109MS311. Included will be the number of subjects with ongoing or resolved medical/surgical history that have occurred since the subject enrolled in 109MS202.

The MS Pediatric Diagnostic Criteria as defined by Krupp (2013), obtained at screening of study 109MS202, will be summarized for those subjects who enrolled into 109MS311.

MS signs considered typical MS signs and symptoms will be summarized for each area: vision, cognition, coordination/balance, bladder control, bowel, sexual function, and general. In addition, MS signs related to sensory disturbances, motor disturbances, and other will be presented for the population and summarized. Only those subjects who entered 109MS311 will be included in the summaries.

History of MS for the subjects enrolled in 109MS311 will be summarized using information collected prior to study 109MS202. This includes time since first MS diagnosis, time since first symptoms, number of relapses prior to screening in study 109MS202 (prior 12 months, 2 years, and 3 years) and the time since the last relapse prior to 109MS202. In addition, the MS treatment history will be summarized for these subjects in 109MS311 prior to receiving BG00012 in the 109MS202 study.

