#### **6.1.6 Exposure to study drug**

Number of days exposed to BG00012 during study 109MS311, total amount of BG00012 received and overall compliance will be summarized. Compliance for each subject is defined as the total amount of BG00012 received divided by the number of days on treatment.

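### The only AE view planned restarts at the first extension dose, so AEs that began on BG00012 in 109MS202 and persist unchanged do not appear in the primary safety summaries

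*SAP*

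**What the plan says.** The primary endpoint in SAP 1.1 is "incidence of AEs, serious AEs (SAEs), and discontinuations of study treatment due to an AE", under an objective of long-term safety in subjects who completed 109MS202. Protocol version 3.0, section 16.1.2.1, turns this into an analysis: "The primary analysis will be summaries of the incidence of treatment-emergent AEs, SAEs, and discontinuations from study treatment due to AEs". Section 16.5.1.1 repeats it.

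SAP 6.3.2.2 defines the emergent events: "Treatment (BG00012)-emergent AEs are defined as AEs occurring or worsening after beginning study treatment (after the first dose in study 109MS311".

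Inclusion criterion 2 (protocol 8.1) requires subjects to have completed 109MS202 and still to be on 240 mg BID. Exposure is also counted within the extension only: SAP 6.1.6 summarizes "Number of days exposed to BG00012 during study 109MS311". SAP 6.1.1 sets baseline at 109MS311 Day 1, and 6.3.2.1 applies that baseline to the safety summaries.

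The nearest the SAP comes to conditions that arose during the parent study is the medical history summary in 6.1.4: "Included will be the number of subjects with ongoing or resolved medical/surgical history that have occurred since the subject enrolled in 109MS202". Neither document plans a table of AEs ongoing at Day 1, or AE incidence counted from the first BG00012 dose in 109MS202.

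**The concern.** In a study where treatment begins on Day 1, excluding events that were already present removes background illness. Here subjects have been on drug throughout the parent study, so the same rule can also remove drug effects.

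The protocol's own adult data make early onset plausible. Section 5.3.2 reports that mean lymphocyte counts fell by about 30% over the first year and then plateaued, and that the excess of transaminase elevations arose mainly in the first 6 months. It also lists flushing and gastrointestinal events among the common AEs. Whether effects that start early go on for a further 96 weeks is a natural part of a long-term safety question. A clinician reading the primary AE table may take it for everything subjects experienced over two more years of treatment. It shows what was new or got worse.

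**Working it through.** The plan states no sample size, AE rate or power figure, so there is nothing to reproduce. The check is definitional, followed by an illustration of size.

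**Tracing one event.** Take an AE with onset on BG00012 in 109MS202 and the same severity to Week 96, in a subject who stays on treatment.

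1. Onset after the first 109MS311 dose (SAP 6.3.2.2)? No.
2. Worsening after that dose? No.
3. Treatment-emergent? No, by 1 and 2.
4. Discontinuation due to an AE? No, because treatment continued.
5. Contribution to the primary summaries in protocol 16.1.2.1: zero.
6. Shown in another planned AE table? None is planned for it. It may appear in the medical history summary of SAP 6.1.4, but that section does not say that parent-study AEs are carried there, and it mentions neither severity nor drug-emergent status.

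**Where the trace stops applying.** An event that worsens counts under step 2. A recurrence recorded as a new event counts under step 1. A carried-over event that ends treatment belongs in the separate discontinuation table of SAP 6.3.2.2.

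**Size for a single AE term.** Let q be the share of subjects with such a persisting event and p the incidence of new or worsened events among the others. Both are assumptions, because the documents give neither. One route to q: if 20% to 40% of entrants had the event in 109MS202 and 25% to 50% of those persist, then q runs from 0.20 × 0.25 = 5% to 0.40 × 0.50 = 20%.

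- Incidence shown = (1 − q) × p
- Incidence including persisting events = q + (1 − q) × p
- Difference = q, whatever p is

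| q (assumed) | Shown, p = 0 | Including persisting, p = 0 | Shown, p = 10% | Including persisting, p = 10% |
|---|---|---|---|---|
| 5% | 0% | 5% | 0.95 × 10% = 9.5% | 14.5% |
| 10% | 0% | 10% | 0.90 × 10% = 9.0% | 19.0% |
| 20% | 0% | 20% | 0.80 × 10% = 8.0% | 28.0% |
| 30% | 0% | 30% | 0.70 × 10% = 7.0% | 37.0% |

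With an assumed 20 subjects, q = 5% to 30% is 1 to 6 subjects. At fixed p, the incidence shown falls as q rises: the more subjects carry the effect in, the fewer can have it emerge.

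**The case against.** The strongest reply is that restarting the emergent clock is ordinary in an extension and that the SAP states it openly. That is correct, and the definition is not an error. It does not explain why no second view is planned when the objective is long-term safety.

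Second, the zero may be less firm than the trace suggests. The endpoint in SAP 1.1 does not say treatment-emergent, the SAP's AE tables do not repeat the restriction, and protocol 15.3.1 asks sites to record "Any AE experienced by the subject between the time of first dose of study treatment in the extension study and the Safety Follow-Up Visit". A site could re-record an ongoing event. This shows an ambiguity, but the protocol's primary analysis is explicitly treatment-emergent, and a re-recorded event with its true onset date would still be excluded.

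Third, laboratory effects are visible elsewhere. SAP 6.3.2.3 summarizes absolute values and lymphocyte counts at each timepoint, and protocol 15.1.1 says that abnormal values are not usually AEs. This largely answers the concern for lymphopenia. It does not help with persistent symptoms such as flushing or gastrointestinal complaints, unless they are recorded as fresh episodes.

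Fourth, integration across the two studies may be planned in documents not provided. Protocol 16.7 foresees periodic summaries for submissions, but describes no integrated AE display.

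Three stronger readings are tempting, and the documents support none of them:

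- *Discontinuations due to AEs are understated too.* Entry excludes "Subjects from Study 109MS202 who could not tolerate study treatment", and accounting starts with "Number of subjects who enrolled into 109MS311 from the previous study". But the objective is limited to completers, so subjects who stopped in 109MS202 lie outside it. Entrants had to complete that study and remain on drug, so counting back to their first dose would add essentially no discontinuations, only time in which none could occur.
- *The SAP assigns parent-study AEs to medical history.* SAP 6.1.4 never says so.
- *Non-serious AEs are lost between the two studies.* The visits are normally combined, SAEs are captured from consent (protocol 15.3.2), and the parent study's recording window is not available.

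**Conclusion.** The point holds in a limited form. Under SAP 6.3.2.2 read with protocol 16.1.2.1 and 16.5.1.1, a BG00012-emergent AE from 109MS202 that persists at the same severity without ending treatment is missing from the primary AE summaries and from every other planned AE table. This rests on the protocol's treatment-emergent wording governing the primary analysis.

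For a given term the shortfall equals the share of subjects with such an event. The 5 to 30 points above are illustrative and have no anchor in the documents. No hypothesis test is affected, since the analysis is descriptive. This is a worthwhile and inexpensive improvement to the safety reporting; it does not correct an invalid method.

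**What to change.** 1. Keep the current table in SAP 6.3.2.2, and label it as new or worsened events in subjects who completed 109MS202 and remained on BG00012. State that the SAP's AE incidence tables use the treatment-emergent definition.
2. Add to 6.3.2.2 a table of BG00012-emergent 109MS202 AEs still ongoing at 109MS311 Day 1, by system organ class, preferred term and severity.
3. Add AE and SAE incidence with onset counted from the first BG00012 dose in 109MS202, for 109MS311 subjects, and add combined 109MS202 plus 109MS311 exposure to 6.1.6. Leave discontinuation as an extension-only figure.

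The cost is SAP wording, some extra programming, and use of AE data from the sponsor's own parent study. The SAP already draws on that study for demographics and medical history. This assumes that the parent AE records hold onset, severity and ongoing status, which the documents do not show. SAP 6.3.2.2 names MedDRA 20.1, so parent terms may need recoding to match. No new data collection is needed. Expect a less favourable AE incidence in the new display, because events from the parent study are counted as well.

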### **6.3.2.3 Clinical Laboratory Data**

The following clinical laboratory parameters are assessed per the protocol:

- Hematology: hemoglobin, hematocrit, red blood cell count, WBC count (with differential) and platelet count.
- Blood chemistry: albumin, sodium, potassium, chloride, total bilirubin, alkaline phosphatase, ALT, AST, GGT, blood urea nitrogen, creatinine, bicarbonate, calcium, magnesium, phosphate, uric acid, and glucose
- Vitamin D and PTH (Day 1 and Week 96 only)
- Urine and serum pregnancy tests

Each laboratory value for each subject will be flagged as ‘low’, ‘normal’, or ‘high’, relative to the parameter’s normal range. Each subject’s urinalysis values will be flagged as “positive”, “negative”, or if no value is available, “unknown”.

Shifts from baseline to post baseline (Week 4/early withdrawal) high/low status for all hematology and blood chemistry parameters, and shifts from baseline to high/positive status for urinalysis will be presented.

Summary statistics will also be provided for all absolute laboratory values as well as change from baseline. The summaries for laboratory data will be data from baseline to each time point, including early withdrawal. Graphs showing the mean or change from baseline values may be presented as well.

In addition to lymphocyte count data summarized at each timepoint on study treatment, lymphocyte count over time post-treatment and the time to recovery will be descriptively summarized for subjects who develop decreases in lymphocyte count (<LLN).

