Overall, safety data from the clinical development program showed that BG00012 was well tolerated and has an acceptable safety profile. In the BG00012 240 mg BID group, the most common adverse events (AEs; incidence $\geq 5\%$) that also occurred at an incidence of $\geq 2\%$ higher than in the placebo group were flushing and hot flush, gastrointestinal (GI) events (diarrhea, nausea, abdominal pain upper, abdominal pain, vomiting, and dyspepsia), skin events (pruritus, rash, and erythema), nasopharyngitis, urinary tract infection, upper respiratory tract infection, albumin urine present, proteinuria, and microalbuminuria. The AE profile was similar for subjects who received 240 mg TID.

In placebo-controlled studies, decreases in mean white blood cell (WBC) and lymphocyte counts were observed over the first year of treatment (approximately 10% and 30%, respectively) with both dose regimens of BG00012. Mean WBC and lymphocyte counts then plateaued and remained stable, even during longer periods of observation of approximately 5.25 years.

Analysis of the data did not show a clear correlation between infections, serious infections, and lymphocyte counts. No increased risk of infection, serious infection, or opportunistic infection was observed in subjects treated with BG00012 in the placebo-controlled studies. With open-label and marketed use of BG00012, progressive multifocal leukoencephalopathy has been observed in the setting of severe and prolonged lymphopenia. There has been no other evidence of increased risk of infections, serious infections, or other opportunistic infections (in open-label and marketed use of BG00012).

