BG00012 was also associated with a small increase in the incidence of elevations of liver transaminases compared to placebo. In the controlled studies, this increase was primarily due to differences that occurred within the first 6 months of treatment. The majority of subjects with elevations had alanine transaminase (ALT) or aspartate transaminase (AST) levels < 3 times the upper limit of normal (ULN). No patients had elevations of ALT or AST $\geq 3 \times$ ULN associated with an elevation in total bilirubin of $> 2 \times$ ULN. There were no cases of hepatic failure due to BG00012. During extended treatment with BG00012, ALT and AST levels remained stable through 3.5 years of observation. Based on these data, there appears to be a transient increase in liver transaminases with BG00012 relative to placebo that does not appear to be associated with any clinically significant liver pathology.

Although the kidney was identified as a target organ of BG00012 toxicity in nonclinical studies, subjects treated with BG00012 in the clinical studies did not appear to have a higher risk of renal or urinary events. Small increases in proteinuria were observed, but the increases did not appear to be clinically significant. On laboratory evaluation, there were no clinically relevant changes in blood urea nitrogen (BUN), creatinine, electrolytes, calcium, phosphorus, parathyroid hormone (PTH), or 1,25-dihydroxyvitamin D. In the Phase 3 studies (Studies 109MS301 and 109MS302), there were no differences between placebo and BG00012 BID in the incidence of proteinuria on 2 consecutive urinalyses (defined as trace or greater) or of 3+ or 4+ protein, both of which are potential indicators of significant proteinuria and renal dysfunction. In addition, there was no evidence of changes over time in $\beta 2$ -microglobulinuria and microalbuminuria, which are more sensitive and specific markers of renal tubular dysfunction, even during longer periods of observation of approximately 3.5 years.

CONFIDENTIAL

The information contained herein may not be used, disclosed, or published without the written consent of
Biogen MA Inc.

In the controlled studies, there was no increased incidence of malignancies in subjects who received BG00012 compared with placebo. The types of malignancies observed and their incidence were within expected background rates.

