AE = adverse event; ALT = alanine transaminase; AST = aspartate transaminase; SGOT = serum glutamic oxaloacetic transaminase; SGPT = serum glutamic pyruvic transaminase; ULN = upper limit of normal; WBC = white blood cell.

[Table 4](#) describes the management of lymphocytes <LLN for subjects during and after study treatment.

CONFIDENTIAL

The information contained herein may not be used, disclosed, or published without the written consent of
Biogen MA Inc.

Table 4: Management of Lymphocyte Count <LLN

Laboratory Parameter	Laboratory Result	Required Action
Lymphocyte count on study treatment	<LLN	The Investigator should repeat the test within 2 weeks. If retest confirms that lymphocyte count is <LLN, lymphocyte count should be closely monitored (at least every 4 weeks).
Lymphocyte count on study treatment	<500/mm ³	If lymphocyte count is <500/mm ³ for more than 6 months, study treatment must be permanently discontinued.
Lymphocyte count in subjects who complete, temporarily withhold, or permanently discontinue BG00012 for any reason	<LLN	Subjects will be followed at least every 4 weeks for 24 weeks and then every 3 months (unless clinically indicated more often or at the Investigator's discretion) until the lymphocyte count is \geq LLN ¹ or for 52 weeks after the last dose, or until one of the following occurs: 1) the subject continues on commercial BG00012 following study withdrawal/completion, or 2) the subject is initiated on another MS disease-modifying therapy.

LLN = lower limit of normal; MS = multiple sclerosis.

¹ Lymphocyte counts \geq LLN at 2 consecutive visits are required.

While dosing is withheld, subjects will continue tests and assessments according to [Table 1](#) (and may also undergo additional assessments to evaluate the laboratory abnormality as per the Investigator's standard practice). In addition, subjects (whether on study treatment, having dosing temporarily withheld, or permanently discontinued) must have the abnormal laboratory result rechecked at the central laboratory as follows:

- For all analytes, with the exception of lymphocytes, results will be rechecked at least every 2 weeks until resolution or stabilization of the laboratory value. Depending on the severity and clinical significance of the abnormality, the Investigator may need to perform the retests more frequently.

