11.2.4. Abnormal Urinalyses That Require Additional Evaluation

Subjects who develop any of the following abnormal urine laboratory values must have the test repeated 2 weeks later:

- urinary casts (other than hyaline casts)
- glycosuria (trace or greater) in the setting of normal serum glucose

If the abnormality persists on retesting, then the subject should be fully investigated for possible causes and referred for evaluation by a nephrologist if appropriate in the opinion of the Investigator.

Subjects who demonstrate 1+ or greater proteinuria on a urine dipstick (and do not have a documented history of prior benign proteinuria) should have a spot protein/creatinine ratio (on AM void). If the spot protein/creatinine ratio is >0.2 mg/mg, then the subject should be fully investigated for possible causes and referred for evaluation by a nephrologist if appropriate in the opinion of the Investigator.

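### No planned laboratory table counts subjects who cross the protocol's own cut-offs, and urinalysis is kept only as positive or negative, so the incidence and duration of severe lymphopenia and worsening proteinuria grade cannot be read from the results

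*SAP*

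**What the plan says.** SAP 6.3.2.3 (Clinical Laboratory Data) classifies blood results against the normal range: "Each laboratory value for each subject will be flagged as ‘low’, ‘normal’, or ‘high". For urine, "urinalysis values will be flagged as “positive”, “negative", or unknown when there is no value. The shift tables rest on these flags. The blood tables are described as "Shifts from baseline to post baseline (Week 4/early withdrawal) high/low status for all hematology and blood chemistry parameters". For urine, the same section promises that "shifts from baseline to high/positive status for urinalysis will be presented".

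The same section also plans summary statistics for absolute values and changes from baseline at each time point. SAP section 6 says such statistics generally include n, mean, SD, median and range. Lymphocytes get further summaries: counts by time point on treatment, counts after treatment, and time to recovery for subjects who fall below LLN.

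The protocol (version 3.0) acts on other limits. For lymphocytes below 500/mm³, Table 4 reads "for more than 6 months, study treatment must be permanently discontinued". Table 3 sets WBC below 2000/mm³, ALT or AST above 3 x ULN and creatinine above 1.2 x ULN. For urine protein, section 11.2.4 begins "Subjects who demonstrate 1+ or greater proteinuria on a urine dipstick" and sends such subjects to a spot protein/creatinine ratio, with 0.2 mg/mg as the limit for further investigation.

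**The concern.** The primary objective is long-term safety. Protocol 5.3.2 explains why depth and duration of lymphopenia matter: "progressive multifocal leukoencephalopathy has been observed in the setting of severe and prolonged lymphopenia". It also names the kidney as a target organ in nonclinical studies. A reader of the final report will want to know how many children fell below 500/mm³, for how long, and whether proteinuria worsened.

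The categorical analysis uses none of the limits that would answer this. The SAP does so elsewhere: section 6.3.2.4 gives explicit thresholds for vital signs and reports the number and percentage of subjects who meet them.

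**Working it through.** No sample size, power or error rate bears on this point, and the plan gives no figure to reproduce. The check asks whether each planned output can yield a per-subject count or a duration.

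**1. Cut-offs against planned counts.**

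| Protocol cut-off | Source (v3.0) | Subject count in SAP |
|---|---|---|
| Lymphocytes <500/mm³ | Tables 4, 5 | none |
| The same for >6 months | Tables 4, 5 | none |
| WBC <2000/mm³ | Table 3 | none |
| ALT/AST >3 x ULN | Table 3 | none |
| Creatinine >1.2 x ULN | Table 3 | none |
| Dipstick protein ≥1+ | 11.2.4 | none |
| Spot ratio >0.2 mg/mg | 11.2.4 | none |

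Protocol 16.5.1.2 does not supply them either.

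**2. Blood shift table.** LLN is not stated. All that is needed is LLN > 500/mm³, which Table 4 implies by treating <500/mm³ as a separate, more severe row. Subjects enter already on BG00012 (inclusion criterion 2), and exclusion criterion 6 removes only counts below 500/mm³. Take a baseline x0 with 500 ≤ x0 < LLN and a later x1 < 500. Both are flagged low, so no shift is recorded. The named post-baseline point, Week 4, is not a scheduled visit in Table 1 of either document, and no worst-value rule is given.

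**3. Urine shift table.** The SAP gives no rule for what counts as positive. With six dipstick grades (negative, trace, 1+, 2+, 3+, 4+) there are 6 x 5 / 2 = 15 possible worsenings. A two-way split with k grades on the negative side shows k(6 − k) of them:
- trace coded positive (k = 1): 5 shown, 10 lost;
- positive from 1+ (k = 2): 8 shown, 7 lost;
- positive from 2+ (k = 3): 9 shown, 6 lost, the best possible.

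If positive starts at 1+ or lower, all 4 x 3 / 2 = 6 worsenings within 1+ to 4+ are lost. Urinalysis is also missing from the parameter list in SAP 6.3.2.3, and no graded summary is requested.

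**4. Per-visit statistics.** This constructed test of what can be recovered is not an estimate for this trial. Take 20 subjects and the 8 haematology visits of protocol Table 1 (Weeks 12 to 96), with 19 values per visit evenly spaced from 950 to 1700 and one at 450.
- Set A: the same subject is at 450 at all 8 visits.
- Set B: eight different subjects are at 450 once each.

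At every visit both sets give n 20, mean (450 + 19 x 1325)/20 = 1281.2, SD 300.6, median 1304.2 and range 450 to 1700. The number flagged low at each visit is the same. If all subjects share one baseline value, the change statistics are identical too. Yet subjects ever below 500/mm³ number 1 in A and 8 in B, and subjects below it at every visit number 1 and 0.

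**5. Visit windows.** Table 4 rechecks confirmed low counts at least every 4 weeks, giving 24 possible rechecks from Week 4 to Week 96. SAP 6.1.7 uses the value closest to target within ±5 days. Rechecks falling in a window are:
- protocol v3.0 haematology visits: 8, so 24 − 8 = 16 lost;
- the SAP's own Table 1, which omits Week 60 haematology: 7, so 17 lost, with a longest gap of 72 − 48 = 24 weeks;
- any scheduled visit: 10, so 14 lost.

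If only windowed values are used, 14 to 17 of 24 rechecks drop out. These are the results that establish duration.

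**6. AE tables.** Table 3 requires an AE record when an abnormality persists and treatment is permanently stopped. Tables 4 and 5 state no such requirement for lymphocytes. Protocol 15.1.1 leaves that to the investigator and says laboratory values are not usually AEs.

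**The case against.** The strongest defence is that SAP 6.3.2.3 does more than flag values, and much of that stands. A reader might infer that blood results are reported only as low, normal or high, or that severe lymphopenia would be invisible. The documents do not support either reading. A scheduled-visit minimum below 500/mm³, or an extreme ALT or creatinine, would appear in the range. A subject stopped for prolonged lymphopenia and still below LLN would enter the post-treatment and recovery summaries, and might be identifiable from the reasons for early withdrawal (SAP 6.1.2). Persistent Table 3 abnormalities reach the AE and discontinuation tables, and a serious clinical consequence would be listed with a narrative. What these outputs lack is the number of subjects and the time spent below the limit. Time to recovery covers everyone below LLN, mild and severe together, and does not measure time below 500/mm³ on treatment.

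A reader might also take high-grade or consecutive-test proteinuria as cut-offs of this protocol, because section 5.3.2 mentions proteinuria on two consecutive tests "or of 3+ or 4+ protein, both of which are potential indicators of significant proteinuria and renal dysfunction". That text reports adult Phase 3 results. The rule to withhold at 2+ stood only in version 1.0. Version 3.0 has the 1+ and spot-ratio trigger for evaluation.

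Finally, the SAP follows protocol 16.5.1.2, the study is descriptive and single-arm, and an IDMC reviews interim safety data. So this is a gap in reporting, not a contradiction between the documents. IDMC review does not put the counts in the final report.

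**Conclusion.** The point holds in a limited form. The plan summarises laboratory values by visit and shifts relative to the normal range, but none of the seven cut-offs listed has a planned subject count, duration below 500/mm³ is not analysed, and dipstick grade is not kept. No planned estimate changes. What is lost is the incidence and duration of severe lymphopenia, and any worsening of proteinuria that stays on one side of the positive/negative line.

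The lymphocyte part assumes only that LLN exceeds 500/mm³. The urine part needs no particular coding rule, since at least 6 of 15 worsenings are lost under any two-way split. The loss of 14 to 17 rechecks depends on summaries using windowed values only, which the SAP does not say outright. Given the primary objective and the low cost, the SAP should be amended.

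**What to change.** In SAP 6.3.2.3:
- Add a worst-post-baseline table using all scheduled and unscheduled results. Show lymphocytes as ≥LLN, 500/mm³ to <LLN, and <500/mm³, with longest continuous time below 500/mm³ and the number of subjects above 6 months. State how the start and end of an episode are dated.
- In the same table, give the number and percentage of subjects meeting each Table 3 blood criterion (WBC, ALT/AST, creatinine).
- Present urine protein as baseline by worst dipstick grade, with the number at 1+ or greater and, where the spot ratio is captured, the number above 0.2 mg/mg.
- Replace the Week 4/early withdrawal shift point with worst post-baseline, and reconcile Week 60 haematology in SAP Table 1 with protocol version 3.0.

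Protocol 10.1 words the lymphocyte duration as 6 months, while Tables 4 and 5 say more than 6 months. These passages must be reconciled before the count is programmed.

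The cost is SAP wording and two or three descriptive tables, with no change to trial conduct. The blood and dipstick results are already collected. The spot ratio is in neither protocol 14.2 nor the SAP list, so its capture must be confirmed. Unscheduled tests are more frequent in subjects already abnormal, which tends to raise worst-value counts in that group. A footnote should say so.
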